We hypothesize an interaction effect of time and intervention group such that the HiBalance group will improve to a greater extent than the active control group on the following outcomes:

Cognitive function

- H5. We hypothesize an interaction effect of time and group such that the HiBalance group will show a greater improvement than the active control group on a composite measure of executive functions. We will base the composite measure on three test measures from the Delis-Kaplan Executive Function System: The verbal fluency test - letter fluency (FAS), The verbal fluency test - category switching (number switches) and the Color-Word Interference Test - switch condition, as well as one test measure from Wechsler Adult Intelligence Scale: Digit Span Total score (forward + backward + sequence) (def. improvement = increased score).

BDNF

- H6. We hypothesize an interaction effect of time and intervention group such that the HiBalance group will show a greater increase than the active control group on mature BDNF.

Brain activity as measured by fMRI during an implicit sequence learning task (the SRTT)

We hypothesize that there will be:

- H7. a group by time interaction effect such that the HiBalance group will show a greater increase in striatal activity, compared to the active control group
- H8. group by time interaction effects in the following frontal areas/ROIs: the primary motor cortex, the premotor cortex, the supplementary motor cortex, the anterior cingulate cortex and the dorsolateral prefrontal cortex (DLPFC). The primary motor cortex, the premotor cortex and the supplementary motor cortex were primarily chosen for their involvement in motor function and the DLPFC and the anterior cingulate cortex were primarily chosen for their involvement in cognitive functions, with important interconnections assumed.

Correlations of individual difference values (pre-post) of behavioural outcomes and BDNF

We hypothesize that there will be:

- H9. a stronger positive correlation between the difference values of the Mini-BESTest and the difference values in mature BDNF within the HiBalance group than within the active control group.
- H10. a stronger positive correlation between the difference values in gait velocity and the difference values in mature BDNF in the HiBalance group than in the active control group
- H11. a stronger positive correlation between the difference values of the composite measure of executive function and the difference values of mature BDNF in the HiBalance group than in the active control group.

Correlations of individual difference values (pre-post) of behaviour outcomes and brain activity

We hypothesize that there will be:

- H12. a stronger positive correlation between the difference values in Mini-BESTest and the difference values of striatal activity within the HiBalance group than within the active control group
- H13. a stronger positive correlation between the difference values in gait velocity and the difference values in striatal activity within the HiBalance group than within the active control group
- H14. a stronger positive correlation between the difference values of the composite measure of executive function and the difference values in striatal activity within the HiBalance group than within the active control group
- H15. stronger correlations between the difference values of the Mini-BESTest and the difference values of activity in the aforementioned ROIs (in H8) within the HiBalance group than within the active control group
- H16. stronger correlations between the difference values of gait velocity and the difference values of activity in the aforementioned ROIs (in H8) within the HiBalance group than within the active control group
- H17. stronger correlations between the difference values of the composite measure of executive function and the difference values of activity in the aforementioned ROIs (in H11) within the HiBalance group than within the active control group

We also expect greater improvements in the HiBalance group compared to the active control group, on the following outcomes:

- Balance confidence as measured by the ABC-scale (def. improvement = increased score)
- MDS-UPDRS III motor part (def. improvement = decreased score)
- MDS-UPDRS total (def. improvement = decreased score)
- Physical activity as measured with the Frändin-Grimby scale (def. improvement = increased score)
- EQ5D-VAS, a measure of self-rated health (def. improvement = increased score)

- PDQ-39 summary index, a measure of difficulties in daily life associated with PD (def.improvement = decreased score)
- HADS anxiety subscale (def.improvement = decreased score)
- HADS depression subscale (def.improvement = decreased score)
- SRTT, a measure of implicit motor sequence learning (def. improvement = greater difference in RT between sequence trials and random trials)

We also expect greater improvements in active control group (HiCommunication) compared to the HiBalance group, on the following outcome:

- Voice intensity, as measured in mean dB during reading of a short story (improvement = higher mean dB). A c-weighted dB outcome will be used as this suppresses low frequent noise.

Analyses

Analyses of behavioural outcomes

The outcomes listed below will be analysed with multilevel models with group, time and the interaction between group and time as independent variables. The models will be specified with the pre and post values as level 1, clustered within the individuals i.e., level 2, with group as a factor on level 2. We will allow for random intercepts but not random slope (due to only two time points). The alpha level will be set to 0.05 for all outcomes. If assumption of normality is not fulfilled, generalized multilevel models will be used and transformations of data will be avoided when possible.

Multiple imputation for cluster level analyses will be used to impute missing values. The primary analyses will be based on the imputed values and all participants included in the study with at least one observed pre or post value will be included. Complementary, we will also perform analyses including solely participants with both pre and post observed values.

- The Mini-BESTest, a measure of balance performance
- Gait velocity, a measure of gait ability measured by a pressure sensitive mat (GAITRite®)
- Step length, a measure of gait ability measured by a pressure sensitive mat (GAITRite®)
- Steps per day, a measure of physical activity level measured by an accelerometer (Actigraph GT3x)
- A composite measure of tests of executive function from the Delis-Kaplan Executive Function System and the Wechsler Adult Intelligence Scale. The composite outcome will be calculated based on a factor analysis on the pre-intervention scores. The final combination of tests to form the composite measure might be modified based on evaluation of the factor model, primarily the fit indices.
- MDS-UPDRS III, a measure of motor ability in PD
- MDS-UPDRS total, a measure of PD symptoms

- The ABC-scale, a measure of balance confidence
- Frändin-Grimby, a measure of physical activity level
- SRTT, a measure of implicit motor sequence learning
- EQ5D, a measure of health and health related quality of life
- PDQ-39, a measure of difficulties in daily life associated with PD
- HADS, a measure of symptoms of depression and anxiety
- dBC during text reading, a measure of voice intensity

Analyses of BDNF

- Mature BDNF will be analysed with multilevel models with group, time and the interaction between group and time as independent variables. The models will be specified with the pre and post values as level 1, clustered within the individuals i.e., level 2, with group as a factor on level 2. We will allow for random intercepts but not random slopes. If assumption of normality is not fulfilled, generalized multilevel models will be used and transformations of data will be avoided when possible. Alpha level will be set to 0.05.
- Multiple imputation for cluster level analyses will be used to impute missing values. The primary analyses will be based on the imputed values and all participants included in the study with at least one observed (pre or post) and usable BDNF sample will be included. Complementary, we will perform analyses including solely participants who had observed and usable BDNF samples for both the pre and post assessments.

Preprocessing and analyses of the fMRI data

Preprocessing

- MRIQC will be used for initial quality control of images.
- The standardized pipeline fMRIPrep will be used for the preprocessing of images. When available, the two T1 images from each individual's pre and post scan will be merged and used as a longitudinal template for co-registration with the functional images. Mapping to standard space will be done using the MNI template 2009c. For individuals with field maps, these will be included in the fMRIPrep pipeline.
- Manual inspection will be done on the MRIQC and fMRIPrep output to determine whether the individuals' data is of sufficient quality for inclusion in the analyses.

First-level analyses (individual-level analyses)

- General linear models will be used to analyse the time-series of brain activity acquired during the SRTT for each voxel, individual and available scan. Independent variables will be the experimental timeline convoluted with the canonical hemodynamic function (HRF) (explanatory variable) and 24

motion parameters as well as aCompCor acquired from the fMRIprep outcome (nuisance regressors). Activity during random blocks will be contrasted to activity during sequence blocks, creating statistical contrast maps for each individual and scan. Structure adaptive smoothing will be performed with default maximum bandwidth.

- Two masks, based on anatomical atlas, will be created and applied to each individual's statistical map(s), one for striatum and one for the remaining ROIs (the primary motor cortex, the premotor cortex, the supplementary motor cortex, the anterior cingulate cortex and the DLPFC).
- Random field theory for small regions with alpha set to 0.05 will be used for thresholding the statistical maps. Thresholding will be done separately for statistical maps of striatum and for statistical maps of the remaining ROIs.

Second-level analyses (group-level analyses)

- To test hypothesis H7, a multilevel model with group, time and the interaction between group and time as independent variables will investigate the group by time interaction effect in the masked statistical map of the *striatum* using a voxel by voxel analysis. There will be no imputation on the fMRI data, but all participants included in the study with at least one (pre or post) times series of brain activity deemed to be of sufficient quality in manual inspection described under "Preprocessing", will be included.
- To test hypothesis H8, multilevel model with group, time and the interaction between group and time as independent variables will investigate group by time interaction effects in the masked statistical map including *the primary motor cortex, the premotor cortex, the supplementary motor cortex, the anterior cingulate cortex and the DLPFC* using voxel by voxel analyses. There will be no imputation on the fMRI data, but all participants included in the study with at least one (pre or post) times series of brain activity deemed to be of sufficient quality in manual inspection described under "Preprocessing", will be included.
- The multilevel models will be specified with the pre and post scans as level 1, clustered within the individuals i.e., level 2, with group as a factor on level 2. We will allow for random intercepts but not random slopes.

Correlations between mature BDNF, brain activity and behaviour outcomes

- For the correlations between mature BDNF and behaviour, we will calculate the within-group correlations between change values (pre-post) in the MiniBESTest, gait velocity and the composite measure of executive function with change values (pre - post) of mature BDNF, using Spearman's rank order correlation. We will correct for multiple comparisons by using the false discovery rate method with alpha set to 0.05. The correlations will be calculated on individuals with data from both the pre and post assessment.
- For the correlations between brain activity and behaviour, we will correlate the within-group change values (pre-post) in the MiniBESTest, gait velocity and the composite measure of executive function respectively, with change values (pre - post) of activity in the ROIs of striatum, the primary

motor cortex, the premotor cortex, the supplementary motor cortex, the anterior cingulate cortex and the DLPFC respectively, using Spearman's rank order correlation. We will calculate the mean activity on the top 10% active voxels of each ROI for each individual's first level contrast map(s). We will correct for multiple comparisons by using the false discover rate with alpha set to 0.05. The correlations will be calculated on individuals with data from both the pre and post assessment.

- To test hypotheses H9:H17, we will perform tests as for whether the within-group correlations between behavioural outcomes and mature BDNF and brain activity change values described above, are significantly larger in the HiBalance group than in the HiCommunication group. This will be done using Fischer's Z significance test. We will correct for multiple comparisons by using the false discover rate set to $p = 0.05$. The corrections will be done separately for our more primary hypotheses i.e., the correlations between mature BDNF and striatal activity with the behavioural outcomes respectively, and the remaining correlations stipulated.
- In addition to testing for group by time effects in mature BDNF, we will investigate group by time interactions for the outcomes proBDNF and the ratio proBDNF/matureBDNF using the same multilevel models as specified for matureBDNF but with an exploratory approach i.e., no hypotheses.
- In addition to testing for group by time effects in the brain areas listed above, we will investigate group by time interactions with a whole brain voxel by voxel analysis, after thresholding with random field theory. We will then correlate change values (pre-post) in the voxels/clusters with significant time by group interactions ($\alpha = 0.05$) with the change values of MiniBESTest, gait velocity and executive function, using Spearman's rank order correlation. Fisher's Z tests will be used to compare the correlation coefficients over the groups.

Planned exploratory analyses

Other information of importance

The preregistration at clinicaltrials.gov NCT03213873 was done before any data collection. The present document of more detailed hypotheses and analyses was formulated after data collection but before analyses. All assessors were blinded throughout pre and post assessments and the author performing the analyses will remain blind to group allocation during the statistical analyses (the two groups have been assigned arbitrary names by a person not involved in the analyses).

References

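### Does the freedom to modify the H5 executive-function composite on factor-model fit call for a stated drop rule and a lock?

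*Combined protocol and SAP*

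**What the plan says.** Under Cognitive function, H5 fixes the starting set. "We will base the composite measure on three test measures from the Delis-Kaplan Executive Function System", namely letter fluency, category switching and the switch condition of the Color-Word test, "as well as one test measure from Wechsler Adult Intelligence Scale: Digit Span Total score". That makes four tests.

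Under Analyses of behavioural outcomes, the SAP says how they are combined: "The composite outcome will be calculated based on a factor analysis on the pre-intervention scores". The next sentence allows a change: "The final combination of tests to form the composite measure might be modified based on evaluation of the factor model, primarily the fit indices". The complementary analysis in the same section concerns missing values only: "Complementary, we will also perform analyses including solely participants with both pre and post observed values".

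The composite is used again in H11, H14 and H17. For those correlations the SAP says: "The corrections will be done separately for our more primary hypotheses". H11 (mature BDNF) and H14 (striatal activity) belong to that favoured family.

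Other information of importance gives the timing, "The present document of more detailed hypotheses and analyses was formulated after data collection but before analyses", and describes the masking of the analyst: "the two groups have been assigned arbitrary names by a person not involved in the analyses".

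**The concern.** An outcome whose components may change after the data are in looks like an open door. The SAP does not say whether the factor analysis is exploratory or confirmatory, how many factors it has, which index and cut-off count as poor fit, which test would then go, or when the set becomes final. The word 'primarily' admits other grounds without naming them.

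The criterion it does name seems unable to do the job: in the simplest case, all the three-test alternatives fit perfectly. Coded group names hide which arm is which, but not whether the two arms differ, so they do not act as a lock. No result with the original four tests is promised if the set changes.

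At stake would be H5, which is part of the first main aim, and three sets of correlations. If the composite were chosen after group-by-time results had been seen, the type I error of H5 would exceed 5%. A reader might also be unable to tell whether a published three-test composite was the one planned.

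**Working it through.** **Inputs.** From the SAP: four tests (H5), 95 participants (Design), alpha 0.05 (Analyses of behavioural outcomes; taken as two-sided). Everything else below is an assumption. The documents give no figure for the composite. Their only sample-size figure, 38 per group under Procedures in the protocol, concerns the Mini-BESTest. It reproduces, 2 × (1.960 + 0.842)² × 3.1² / 2² = 37.7, rounded up to 38, but it does not bear on this point.

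**1. What fit can and cannot decide.** A one-factor model on p tests with free loadings and uncorrelated residuals has p(p+1)/2 − 2p degrees of freedom.
- Four tests: 10 − 8 = 2.
- Three tests: 6 − 6 = 0.

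In one simulated baseline sample of 95 with clear misfit, the four-test chi-square was 8.84 on 2 df, so RMSEA = √((8.84 − 2)/(2 × 94)) = 0.19. Dropping any one of the four tests gave a chi-square of 0.00 on 0 df. Fit ranks the four choices equally.

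This result is conditional. With equal loadings the degrees of freedom are 10 − 5 = 5 for four tests and 6 − 4 = 2 for three. Swapping one test for another keeps 2, and adding a fifth gives 15 − 10 = 5. The SAP neither adopts nor excludes any of these.

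**2. How often the four-test model would be flagged.** RMSEA exceeds c when chi-square exceeds 2 + 2c²(N − 1). On 2 df the chance of that under a true model is exp(−x/2). With N = 95:
- c = 0.06: x = 2.68, chance 26%.
- c = 0.08: x = 3.20, chance 20%.
- c = 0.10: x = 3.88, chance 14%.

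The unstated cut-off therefore matters for whether a change is triggered.

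**3. Type I error.** Randomisation makes group label independent of baseline scores, so a choice based on pooled baseline scores cannot favour a group difference in change. Simulation (48 v 47, 20,000 runs, correlations between test change scores of 0.1 to 0.5) gave:
- Composite fixed, or picked at random without looking at outcomes: 0.049-0.053.
- Best of five composites (all four tests, or any three) picked after seeing results: 0.089-0.125.
- Best of eleven (any two or more tests), picked likewise: 0.136-0.203.

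Only a choice made after the results are seen inflates the error, and the SAP describes no such choice.

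**4. Effect on the conclusion.** The trial would report one modified composite, so the relevant comparison is four tests against one three-test set. The assumptions are 47 v 48, retest correlation 0.75, equal weights, a t-test on difference in change, and several loading patterns: all 0.55, with and without a residual correlation of 0.3 between the fluency tests; three strong tests and one weak; all 0.70. At a factor effect of 0.3-0.5 SD, the two composites fall on different sides of p<0.05 in 5-14% of trials. Counting disagreement by any of the candidate sets gives 15-37%, but that is not what a reader of the trial would meet. The 5-14% also counts trials in which the four-test model is never flagged, so the share actually affected is smaller.

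**5. Power at 0.5 SD, factor weights.** With all loadings 0.55, power falls from 75% to 67-70% when a test is dropped. With one test loading 0.16, it stays at 79% if that test is dropped and falls to 64-65% if another is. The direction is not fixed.

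**The case for a change.** The best case for a change is this. Each missing item is truly missing. Baseline scores are the stated basis, but 'primarily' leaves room for other grounds. Coded labels do not conceal the size of a group difference. The statement on timing dates the SAP and not the composite. The composite reaches H11 and H14 in the favoured correlation family. The cost would be a few sentences and one repeat analysis.

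Most of those facts stand. What does not follow is that the plan would give a wrong answer. The SAP places the factor analysis on pre-intervention scores, and analysts would ordinarily settle a composite before modelling it. 'Evaluation of the factor model' naturally includes loadings and test content, so the SAP does not claim that fit alone decides. The four planned tests are on record in H5, so any departure from them can be seen.

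Nor is a mechanical rule clearly better than judgement. Take a loading cut-off in a four-test model that allows the two fluency tests a residual correlation. In 400 simulated samples of 95, that model gave improper solutions in 53% when the fourth test loaded 0.16 and in 24% when it loaded 0.30. With all true loadings at 0.55, an assumed cut-off of 0.40 flagged at least one good test in 39%. Repeating H11, H14 and H17 with four tests would also raise the question of whether the repeats enter the false-discovery-rate families.

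**Conclusion.** No change is needed. The SAP leaves out the model, index, cut-off, drop rule and time of decision, and under one factor with free loadings and uncorrelated residuals, fit cannot choose which single test to drop. This is missing detail that analysts can fill sensibly. A choice on baseline scores by an analyst who does not know which group is which keeps H5 at about 5%, and power can move either way. A change of set would alter the p<0.05 call against the four-test composite in about 5-14% of trials under the assumed loadings, retest correlation and effects of 0.3-0.5 SD. A dated lock and a four-test repeat would make a secondary outcome easier to trace, but would not correct a wrong result.

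The conclusion rests on the choice being made from baseline scores, as the SAP describes. If it were made after sight of group-by-time results, the error would be about 9-13% over five candidate composites and 14-20% over eleven, and the judgement would differ.

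### Does leaving the sign of the random/sequence fMRI contrast unstated undermine the top-10% voxel measure and the directional brain hypotheses?

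*Combined protocol and SAP*

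**What the plan says.** In the SAP section *First-level analyses*, the contrast is described in one clause: "Activity during random blocks will be contrasted to activity during sequence blocks". One map results per person and scan. No subtraction order or weights are given. The maps are then masked, and "Random field theory for small regions with alpha set to 0.05 will be used for thresholding the statistical maps".

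The hypotheses that use these maps differ in how directional they are:
- H7 predicts that "the HiBalance group will show a greater increase in striatal activity, compared to the active control group".
- H12 predicts "a stronger positive correlation between the difference values in Mini-BESTest and the difference values of striatal activity within the HiBalance group" than in the control group. H13 and H14 have the same form.
- H8 names no direction. H15-H17 predict stronger correlations but do not say positive.

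In *Correlations between mature BDNF, brain activity and behaviour outcomes*, the regional measure is defined: "We will calculate the mean activity on the top 10% active voxels of each ROI for each individual's first level contrast map(s". Change is pre minus post for both behaviour and brain activity, and the correlation is Spearman's. A Fisher Z test then asks whether the correlations "are significantly larger in the HiBalance group than in the HiCommunication group", with false discovery rate control. The correction is done separately for "our more primary hypotheses i.e., the correlations between mature BDNF and striatal activity with the behavioural outcomes respectively" and for the rest.

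The only direction stated for the task itself concerns reaction time, in the list of further expected improvements. *Other information of importance* says the SAP was written after data collection but before analysis, and that the analyst works blind to group.

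**The concern.** An increase in a contrast has no meaning until one knows which condition is subtracted. Coded one way, H7 predicts more striatal activity in sequence blocks relative to random blocks. Coded the other way, it predicts the reverse. The SAP defines improvement for its behavioural outcomes but gives no equivalent for brain activity.

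For a whole-region mean this would be trivial, since reversing the contrast only reverses the sign. The planned measure keeps only the most active tenth of voxels. Under signed ranking, the top tenth of a map and the top tenth of its negative are opposite tails, so one result cannot be converted into the other. The measure feeds every comparison in H12-H17, and H12-H14 sit in the family the SAP ranks higher. Two analysts could therefore report different findings from the same scans. It also looked open whether the tenth is taken before or after thresholding, whether activity means a contrast estimate or a t or z value, and whether the voxels are chosen per scan or once.

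**Working it through.** **Reach.** H12-H14 pair 3 behaviours with 1 region (striatum), giving 3 comparisons. H15-H17 pair 3 behaviours with 5 regions, giving 15. The regional measure enters all 18, but a positive direction is predicted in only 3. H7 is the one other directional brain hypothesis.

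**Sample size used below.** The protocol's *Procedures* section gives SD 3.1, difference 2, alpha 0.05 and power 80%. Then n = 2 × [3.1 × (1.960 + 0.842)/2]² = 37.7, so 38 per group, as stated. This is the Mini-BESTest target. The number with two usable scans is not given, so 38 is an assumption here.

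**Voxels held fixed.** Assume correlations of 0.4 and 0:
- Z = [atanh(0.4) − atanh(0)]/√(2/35) = 0.424/0.239 = 1.77.
- One-sided p = 0.038. With the contrast reversed, Z = −1.77 and p = 0.962.
- Two-sided p = 0.076 under either sign.

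Taking change as pre minus post does not matter, because it reverses both variables and leaves the correlation unchanged.

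**H7.** Reversing the contrast multiplies the group-by-time coefficient by −1 and leaves its standard error alone. A two-sided test has the same p-value. Only the reading of a significant result, as support or contradiction, depends on the sign.

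**Top-tenth rule.**
- Ranked by signed value: the two signs select opposite tails, with 0% of voxels shared.
- Ranked by absolute value: both signs select the same voxels, and the mean signed value simply reverses.

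The SAP does not say which ranking applies, so the disjoint-voxel result is conditional on signed ranking.

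**Illustration only.** The documents give no fMRI figures, so all inputs to this simulation are assumed (38 people, 1,000 voxels, 150 runs, signed ranking per scan). If the effect lies in a subregion more active in sequence blocks, the mean Spearman correlation with behaviour is about 0.61 for sequence minus random and −0.07 for the reverse. If the effect is uniform over the region, it is 0.38 and −0.38. The first case shows a different measure. The second shows a plain sign change. The documents cannot say which applies.

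**The remaining choices, read against the text.**
- *Sign:* random blocks are set against sequence blocks, in that order. Taken literally this is random minus sequence, though the hypotheses do not refer back to it.
- *Threshold:* the correlation section takes a tenth of each region, not of surviving voxels, and refers to the first-level contrast maps. The whole-brain analysis, in contrast, is explicitly described as following thresholding. The natural reading is unthresholded maps.
- *Voxel set:* maps are made per person and scan, and the tenth is taken from each person's map or maps. That reads as per scan.
- *Units:* contrast estimate or t/z value is open.

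**The case for a change.** The strongest case for a change runs as follows. The SAP was written after the data were in, so fixing choices before results are seen is the main safeguard left. Blinding to arm does not define a measure. The task is presented as one of sequence learning, so the literal random minus sequence may not be what H7 intends. Linking clinical change to brain change is the project's main aim, and two added sentences would settle the matter.

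Much of this stands. The omission is real, and under signed ranking it affects the measure as well as the sign. It does not amount to an undefined direction, because the word order gives one reading and any analyst must fix a sign to fit the model at all.

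The risk of choosing after the fact has been simulated, again with assumed inputs. One unadjusted two-sided test at 0.05 has a false-positive rate of 0.09-0.10 if the better of the two signs is picked. The rate is 0.30-0.33, as an upper bound, if the best of all 16 combinations of sign, units, threshold and voxel set is picked. An analyst blind to group cannot steer the result towards HiBalance. By symmetry about half of these would favour it: 0.045-0.05 and 0.15-0.165. Those figures also leave out the planned false discovery rate control and presume deliberate selection, which nothing in the plan invites.

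The published study protocol to which the SAP refers may define the contrast. It is not among the documents, so no weight is placed on it.

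**Conclusion.** No change to the plan follows. The sign of the contrast, the ranking rule and the units are details that the analyst must settle to run the models and would state when reporting them. For the map and the voxel set, the text already points to unthresholded maps and selection per scan. No rule written in the SAP is shown to give a wrong result, and no better method is at issue, since filling these gaps leaves the planned top-10% measure and tests as they are.

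The consequences are limited. For H7, only the interpretation of a significant result depends on the sign. For H12-H14 (3 of 18 comparisons), the predicted direction depends on it. For H12-H17 as a whole, the voxels measured depend on it only if ranking is signed. H8 is not directional, and H1-H6 and H9-H11 do not use the contrast.

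This rests on the sign being set once, for all scans, by an analyst still blind to group, as the SAP provides. The p-values of 0.038 and 0.962 rest on assumed correlations and 38 per arm. The simulated figures are illustrations, not estimates for this trial.
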